IBD	Inflammatory Bowel Disease
ICH	International Council on Harmonization
IEC	Independent Committee
IGA	Investigator's Global Assessment
IHC	Immunohistochemistry
IRB	Institutional Review Board
IRT	Interactive Response Technology
ISF	Investigator Site File
IUD	Intrauterine Device
IUS	Intrauterine Hormone-Releasing System
LLOQ	Lower limit of quantification
LPLT	Last Patient Last Treatment
MedDRA	Medical Dictionary for Drug Regulatory Activities
MMRM	Mixed model with repeated measurements
Nab	Neutralizing Antibody
NOAEL	No-observed-adverse-effect level
OPU	Operative Unit
PBMC	Peripheral blood mononuclear cell
PK	Pharmacokinetics
PPP	Palmoplantar Pustulosis
RA	Regulatory Authority
RCTC	Rheumatology Common Toxicity Criteria
REML	Restricted maximum likelihood
REP	Residual Effect Period
s.c.	subcutaneous
SAE	Serious Adverse Event
SAF	Safety Analysis Set
SD	Standard Deviation
SCORAD	SCORing of Atopic Dermatitis
SoC	Standard of Care

Proprietary confidential information © 2020 Boehringer Ingelheim International GmbH or one or more of its affiliated companies

SOP	Standard Operating Procedure
SUSAR	Suspected Unexpected Serious Adverse Reactions
TMDD	Target-Mediated Drug Disposition
TSAP	Trial Statistical Analysis Plan
ULN	Upper Level of Normal
ULOQ	Upper limit of quantification
WHO	World Health Organization
WOCBP	Woman of childbearing potential

1. INTRODUCTION

1.1 MEDICAL BACKGROUND

Atopic Dermatitis (AD) is an immune-mediated skin disease characterized by chronic or relapsing red and inflamed skin (erythema) and an intense and unrelenting itch (pruritis). In common terminology AD is often referred to as Eczema, the term for a variety of skin conditions, of which AD is the most severe. Diagnosis is based on a patient's medical history, characteristic clinical findings and exclusion of other skin conditions [[P18-07868](#)]. The hallmark of AD is pruritus that is responsible for much of the disease burden for patients and their families. Pruritus can be persistent and consequently can disrupt sleep and/or cause anxiety or depression [[R18-2681](#), [R18-2680](#)]. Other clinical features of AD include skin dryness, erythema (redness), oozing, crusting, and lichenification (skin that has become thickened and leathery).

Worldwide, the lifetime prevalence of AD has increased over the last 30 years occurring in 10–20% of the population in developed countries. Prevalence is lower, but increasing, in developing countries [[R18-2667](#)]. Typically, AD develops during childhood with approximately 60% of cases occurring in the first year of life [[P06-08156](#); [R18-2668](#)]. In about 70% of cases, the disease greatly improves or resolves in childhood, but the remaining 30% of patients go on to have a remitting and relapsing condition with repeated flares [[R18-2668](#); [R18-2663](#)].

AD appears to have a more heterogeneous pathophysiology than previously thought. Unlike chronic plaque psoriasis that is almost exclusively driven by the Th17 pathway, AD involves multiple immune axes involving expression of multiple cytokines and chemokines, including IL-13, IL-4, IL-33, IL-17 and IL-22. IL-36 is thought to have a pivotal role in amplifying these immune pathways and may be a critical link between *S. aureus* infection and exacerbation of AD inflammation.

In human skin tissues, IL36R is expressed in keratinocytes, dermal fibroblasts and infiltrating myeloid cells. IL36R activation in skin tissue drives the production of inflammatory mediators (e.g. CCL20, MIP-1 β , TNF- β , IL12, IL17, IL23, TGF- β) and modulates the expression of tissue remodeling genes (e.g. MMPs, TGF- β). The link between IL36R and AD is based on data demonstrating upregulation of human IL36R and IL36 γ (and IL36 α) expression in AD skin biopsies compared to normal control skin as well as data showing IL36R functionality in disease relevant primary human cells. In addition, there is data demonstrating enhanced IL-36 signaling in human macrophages via the TH2 cytokine (IL4) pathway.

Recent data suggest that IL36R may also play a role in the pathogenesis of AD via a specific pathway related to *S. aureus* infection [[R18-2666](#), [R18-2669](#)]. These papers show epicutaneous infection with *S. aureus* induces an inflammatory response mediated by IL-36 pathway and that IL36R deficiency or blockade results in a reduction of the skin inflammation induced by *S. aureus* derived virulent PSM α peptides [[R18-2666](#), [R18-2669](#)]. These studies demonstrated a clear link to the IL36 pathway suggesting IL36 pathway activation may represent an early and persistent event in the development of AD disease.

1.2 DRUG PROFILE

1.2.1 Mode of Action

BI 655130 is a humanized antagonistic monoclonal IgG1 antibody that blocks human IL36R signaling. Binding of BI 655130 to IL36R is anticipated to prevent the activation of IL36R by cognate ligands (IL36 α , β and γ) and subsequent downstream activation of pro-inflammatory and pro-fibrotic pathways with the aim to reduce epithelial cell/ fibroblast/ immune cell-mediated inflammation and interrupt the inflammatory response that drives pathogenic cytokine production in inflammatory diseases including AD, generalized pustular psoriasis (GPP), palmoplantar pustulosis (PPP) and inflammatory bowel disease (IBD).

1.2.2 Nonclinical pharmacology

Preclinical studies

BI 655130 binds to human IL36R with a binding avidity of less than 1 pM. BI 655130 inhibits IL36 ligand-stimulated NF- κ B activation in HT29 and transformed epithelial cells and in primary human dermal fibroblasts or intestinal myofibroblasts with IC90 values in a consistent range of 0.7 to 3.7 nM. BI 655130 also inhibits IL8 release in primary human intestinal myofibroblasts and IFN γ secretion in human peripheral blood mononuclear cell (PBMC) stimulated with IL36 α , IL36 β , or IL36 γ combined with IL12.

Mutations of two key residues (L234 and L235) to alanine were made to BI 655130 to abrogate FcR binding activity and function. Direct assessment of the impact of the mutations in the IgG1 FcR binding sites on both antibody-dependent cellular cytotoxicity (ADCC) and complement-dependent cytotoxicity (CDC) effector functions revealed that the mutations abrogate both ADCC and CDC effector functions and indicate that BI 655130 will be a non-depleting therapy in vivo.

Toxicology studies

As BI 655130 does not demonstrate adequate pharmacological activity in common toxicology species, a surrogate antibody (BI 674304) specific for mouse IL36R was developed and used for toxicology assessments. In a 13-week intravenous toxicity study of BI 674304 in mice, no adverse effects of IL36R antagonism were seen at a dose (50 mg/kg, twice weekly) that was 5 fold higher than the dose that was protective in an experimental mouse colonic inflammation model. The in vitro cytokine release and tissue cross-reactivity assays demonstrate that the risk of transient cytokine release in humans is low and that, as expected, BI 655130 stains epithelium in a variety of tissues. There were no signs of local irritation after single, 1 mL injections of the subcutaneous formulation in rabbits.

In intravenous toxicity studies of up to 26 weeks in duration in mice, no adverse effects of IL36R antagonism were seen at a dose that was 5 fold higher than the dose predicted for human studies. Based on these results, the no-observed-adverse-effect level (NOAEL) was considered to be 50 mg/kg/dose.

In developmental and reproductive toxicity studies there was no evidence of effects on fertility or embryonic development in mice after administration of 50 mg/kg/dose of BI 674304 in directed fertility and embryonic development studies.

1.2.3 Clinical experience

As of April 2019, five clinical phase I trials and one clinical phase II trial have been completed for BI 655130; 4 phase I trials were conducted in healthy volunteers (HV), 1 phase I trial in GPP patients and 1 phase II trial in PPP patients.

A total of 187 healthy volunteers have been exposed to single or multiple doses of BI 655130 in 4 phase I studies which assessed safety, tolerability, PK and PD of BI 655130 in healthy volunteers [c09985235-01].

- Study 1368.1 was a single escalating dose trial with i.v. infusions of placebo or BI 655130 up to 10 mg/kg [[c09985235-01](#)]. The most frequently reported treatment-emergent AEs were nasopharyngitis (BI 655130: 20.7%; placebo: 15.0%), headache (BI 655130: 8.6%; placebo: 15.0%), influenza like illness (BI 655130: 6.9%; placebo: 10.0%), and diarrhoea (BI 655130: 3.4%; placebo: 10.0%). All AEs were of mild or moderate intensity and were resolved by the end of the trial. There were no serious AEs and no AEs that led to discontinuation of trial drug.
- Study 1368.2 was a multiple rising dose trial with subjects receiving up to 20 mg/kg in a single intravenous infusion weekly for 4 weeks. The incidence of nervous system disorders (especially headache) appeared to be higher in the 20 mg/kg BI 655130 group than in the other treatment groups. Two subjects experienced dyspnoea only in the 20 mg/kg group. Additionally, gastrointestinal disorders (diarrhoea and nausea) and nasopharyngitis appeared to occur more often in subjects who received BI 655130 than in subjects who received placebo. Infusion related reaction, decreased appetite, and anxiety were reported for 1 subject in the 20 mg/kg BI 655130 treatment group.
- Study 1368.3 was a relative bioavailability trial in 36 subjects of a subcutaneous (s.c.) formulation of BI 655130 at two different dose strengths (150 mg and 300mg). The most frequent local events reported were redness and swelling at the injection site, all were mild in intensity, occurred within 30 minutes after injection and completely resolved within 4 hours. There were no reports of injection site pain.
- Study 1368.9 was a single rising dosing trial in 32 Japanese healthy volunteers receiving different i.v. doses of BI 655130 (300 mg, 600 mg, and 1200 mg) or one subcutaneous dose (300 mg). Adverse events by preferred term reported on placebo were vomiting, chest discomfort, and allergic rhinitis, while AEs reported on BI 655130 were upper respiratory infection (300 mg i.v.), contusion (600 mg i.v.), gastroenteritis (1200 mg i.v.), and temporomandibular joint syndrome (1200 mg i.v.). None of the observed AEs were judged by the investigator as related to the trial medication.

The first study in patients was conducted as an open-label, single arm phase I study to explore the safety, tolerability, PK and efficacy of BI 655130 in GPP (1368.11). A total of 7 patients with acute GPP were enrolled and treated with a single intravenous dose of BI 655130 (10 mg/kg). Proof-of-concept was achieved with the first 7 patients treated, who showed rapid clinical responses to single administrations of BI 655130 with good safety and

tolerability. The early response in the skin was also accompanied by an early and rapid response in systemic components (C-Reactive Protein [CRP] approaching normalization within 4 weeks). All patients (7/7) reported at least 1 AE while on-treatment and in 4 patients (57.4%) AEs considered drug-related by the investigators were reported. None of the reported AEs was severe, serious or led to discontinuation. The most frequently reported treatment-emergent AE was arthralgia (3 out of 7 patients [42.9%]). Eosinophilia, chills, oedema peripheral, pyrexia, upper respiratory tract infection, and eczema were each reported in 2 patients [28.6%]

Study 1368.15, a randomised placebo controlled study investigated the safety, tolerability, pharmacokinetics, pharmacogenomics and efficacy of 2 intravenous doses of BI 655130 in 59 patients with palmoplantar pustulosis psoriasis. Patients were randomized in a 1:1:1 allocation ratio and received either 900 mg BI 655130, 300 mg BI 655130 or placebo intravenously every 4 weeks over a period of 12 weeks. The proportion of patients who achieved ppPASI50 at Week 16 in the total population was similar in all treatment groups (6 of 19 in 900 mg BI 655130 arm, 6 of 19 in 300 mg BI 655130 arm, and 5 of 21 in placebo arm). However, post-hoc subgroup analyses indicated efficacy of both doses of BI 655130 in patients with more severe PPP disease at baseline (above the median PPPASI value of 16.7). In particular, the results on pustule severity were pronounced with a rapid reduction in pustule severity with evidence of a dose response relationship.

In total, 85.7% in the placebo arm and 89.5% in each of the BI 655130 arms (300 mg and 900 mg) reported at least 1 AE while on treatment. There were 3 AEs leading to discontinuation of trial drug in the placebo arm (14.3%), whereas 1 patient in the 300 mg dosing arm (5.3%) and 3 patients in the 900 mg dosing arm (15.8%) discontinued trial medication due to an adverse event. The most frequently reported treatment-emergent AE were nasopharyngitis (placebo 38.1%, 300 mg BI 655130 26.3%, 900 mg BI 655130 42.1%) and headache (placebo 33.3%, 300 mg BI 655130 21.1%, 900 mg BI 655130 31.6%).

PK data indicate target-mediated drug disposition (TMDD) of BI 655130. The saturation of the non-linear elimination pathway is likely occurring after 0.3 mg/kg and BI655130 exhibits linear kinetics at dose-level greater than 0.3 mg/kg. The half-life of BI655130 is approximately 4 weeks in the linear dose range and thus similar to other IgG1 molecules.

In one patient an infusion related reaction was reported. The patient felt “heat” after the infusion of the trial medication during Visit 3. The event was not accompanied by other symptoms, in particular vital signs remained stable. The patient recovered without treatment. There were no clinically relevant abnormalities on treatment with BI 655130 with respect to safety laboratory and vital signs.

Summary

BI 655130 has been tested and found safe and tolerable in humans in single and multiple rising dose trials 1368.1, 1368.2, 1368.3 and 1368.9 in healthy male and female subjects and in trial 1368.11 in GPP patients and in trial 1368.15 in PPP patients. The most frequently reported treatment-emergent AEs were viral upper respiratory tract infection, nasopharyngitis, headache, influenza like illness and injection site erythema, without any dose-dependency. One potential infusion reaction has been reported in a subject who

discontinued his third infusion of BI 655130 in 1368.2. All AEs were resolved by the end of the trial. There were no relevant changes in safety laboratory tests, vital signs, or ECGs

For further details and most up-to-date results refer to the current "Investigator's Brochure" [\[c03320877-05\]](#).

1.3 RATIONALE FOR PERFORMING THE TRIAL

Although the pre-clinical data and rationale for the use of an IL-36R antagonist in AD are strong, there are no clinical data on this mechanism of action in AD. Thus, a small proof of clinical concept study is planned to assess safety, tolerability and efficacy in patients with moderate to severe AD.

In order to be able to address future scientific questions, patients will be asked to voluntarily donate biospecimens for banking (please see Section [5.4](#)). If the patient agrees, banked samples may be used for future biomarker research and drug development projects, e.g. to identify patients that are more likely to benefit from a treatment or experience an adverse event (AE), or to gain a mechanistic or genetic understanding of drug effects and thereby better match patients with therapies.

1.4 BENEFIT - RISK ASSESSMENT

The positive efficacy data obtained in GPP (trial 1368.11) confirms BI 655130's mechanism of action of effectively blocking the IL36 pathway thereby providing support for potential benefit in diseases where the IL36 pathway appears to contribute to disease. Furthermore, the clinical safety data support clinical studies in patients with repeat doses up to 20mg/kg IV qw.

There is no direct benefit for individual participants in this study, because efficacy of BI 655130 has not been demonstrated in AD and because some patients will initially be randomised to the placebo arm. Participation in this study may help to generate future benefit for larger groups of patients with atopic dermatitis if BI 655130 proves to be successful in treating this disease. In order to assess any future benefit for atopic dermatitis patients, it is critical to have a placebo control to address potential confounding factors, such as placebo effect, regression to the mean in endpoint scoring or potential investigator bias in safety and efficacy assessments. Patients who are initially randomized to placebo and do not respond will be given the opportunity to receive BI 655130 after the Week 16 primary analysis.

One subject in trial 1368.2 appeared to have an infusion reaction at a dose of 20 mg/kg, thus patients in this trial will be closely monitored for infusion reactions, including measurement of pulse and blood pressure prior to infusion and approximately 5 and 60 minutes after the end of infusion.

Humans with congenital absence of IL36R have no adverse clinical signs or symptoms, including susceptibility to infection or reactivation of chronic infections. Nonetheless, given this is the first trial in patients with atopic dermatitis, patients with active infection or certain chronic infections (HIV, HBV, TB) will be excluded.

Proprietary confidential information © 2020 Boehringer Ingelheim International GmbH or one or more of its affiliated companies

The mouse specific analogue of BI 655130 has been tested in embryo-fetal and fertility and early embryonic development studies. There was no evidence of effects on fertility or embryonic development (teratogenicity) in mice after administration of 10 or 50 mg/kg/dose.

Thus, men and women of child bearing potential with appropriate birth control can be included in clinical trials with BI 655130. Women of child bearing potential with appropriate birth control can be included in clinical trials with BI 655130 but must maintain a highly effective method of contraception throughout the course of trials with BI 655130 and up to 16 weeks after the last study drug infusion. Contraception of male trial precipitants and female partners of male trial participants are not required based on the toxicity studies conducted in mice. Due to the outcome of the completed teratogenicity study a double barrier method of contraception is not required.

Currently there are no data available allowing the conduct of clinical trials in pediatric patients, pregnancy and lactation. Until such data are available, these patients will be excluded from this study (1368-0032).

Currently there are no data available to suggest interactions of BI 655130 with other drugs [[c03320877-05](#)].

Considering the medical need for development of an effective and well tolerated drug for the therapy of AD, the benefit of this trial is considered to outweigh the potential risks and justifies the administration of multiple doses of BI 655130 to patients with AD to investigate safety, tolerability and efficacy.

2. TRIAL OBJECTIVES AND ENDPOINTS

2.1 MAIN OBJECTIVES, PRIMARY AND SECONDARY ENDPOINTS

2.1.1 Main objectives

The primary objective of this trial is to investigate the safety, tolerability and efficacy of BI 655130 in patients with AD following multiple intravenous administrations of 600 mg compared to placebo.

While the main objective is to assess safety and tolerability of BI55130 in patients with AD, these endpoints can only be analyzed descriptively. Thus, the endpoints to be discussed below will focus on efficacy endpoints that are more amenable to other statistical analyses and where sample size considerations may be more relevant.

A description of the endpoints to be determined, and the observations along with specific information as how to collect the data for that information, is provided in Section [5](#).

[figure not shown]
2.1.2 Primary endpoint

The primary efficacy endpoint for this trial is the percentage change from baseline in the Eczema Area and Severity Index (EASI) Score at Week 16.

[figure not shown]
2.1.3 Secondary endpoint(s)

Secondary efficacy endpoints are

- Number of patients with drug related AEs
- Absolute and percentage change from baseline in EASI at Week 4
- Proportion of patients with a 50% improvement from baseline in EASI (EASI50) at Week 4 and 16
- Proportion of patients with a 75% improvement from baseline in EASI (EASI75) at Week 4 and 16
- Change from baseline in SCORAD at Week 4 and 16
- Proportion of patients achieving at least a 2-grade reduction from baseline to clear (0) or almost clear (1) in IGA at Week 4 and 16

Proprietary confidential information © 2020 Boehringer Ingelheim International GmbH or one or more of its affiliated companies

3. DESCRIPTION OF DESIGN AND TRIAL POPULATION

[figure not shown]
3.1 OVERALL TRIAL DESIGN AND PLAN

This is a double-blind, placebo-controlled study assessing the safety, tolerability and efficacy of 600 mg BI 655130 compared to placebo given intravenously every 4 weeks in patients with moderate to severe atopic dermatitis. Safety and tolerability will be evaluated based on AE data collected and physical examination at every visit. At W16 patients will be evaluated for response to treatment by the change in EASI score compared to baseline. Patients who have responded, defined as having attained at least 75% reduction in EASI score compared to baseline will no longer receive treatment and will be followed at W 20, 24 and 28 to evaluate the sustainability of their response. If this patient reaches a 50% reduction in EASI score compared to baseline prior to the planned EOS at Week 28, they will immediately perform EOS and will be given the opportunity to receive treatment in an open label extension trial.

Patients who have not responded, defined as attained less than 75% reduction in EASI score compared to baseline will receive 600 mg BI 655130 at W16, 20, 24 and 28. Patients re-allocated to treatment, who reach EOS will be offered participation in the extension trial if they meet the eligibility criteria.

After re-allocation at Week 16, a patient will know what treatment they are on but will remain blinded to the treatment received until Week 16.

Figure 3.1.1 Trial design

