5.2.5.2 Adverse event collection and reporting

AE Collection

The investigator shall maintain and keep detailed records of all AEs in the patient files.

The following must be collected and documented on the appropriate CRF(s) by the investigator:

- From signing the informed consent onwards until the individual patient's end of trial:
 - all AEs (serious and non-serious) and all AESIs
- After the individual patient's end of trial:
the investigator does not need to actively monitor the patient for new AEs but should only report any occurrence of cancer and related SAEs and related AESIs of which the investigator may become aware of by any means of communication, e.g. phone call.
Those AEs should however not be reported in the CRF.

AE reporting to the sponsor and timelines

The investigator must report SAEs, AESIs, and non-serious AEs which are relevant for the reported SAE or AESI, on the BI SAE form immediately (within 24 hours) to the sponsor's unique entry point (country specific reporting process will be provided in the ISF). The same timeline applies if follow-up information becomes available. In specific occasions, the investigator could inform the sponsor upfront via telephone. This does not replace the requirement to complete and send the BI SAE form.

With receipt of any further information to these events, a follow-up SAE form has to be provided. For follow-up information the same rules and timeline apply as for initial information.

Information required

For each AE, the investigator should provide the information requested on the appropriate eCRF pages and, if applicable, the BI SAE form. The investigator should determine the causal relationship to the trial medication.

The following should also be recorded as an (S)AE in the CRF and, if applicable, BI SAE form:

- Worsening of the underlying disease or of other pre-existing conditions.
- Changes in vital signs, ECG, physical examination and laboratory test results, if they are judged clinically relevant by the investigator.

If such abnormalities already pre-exist prior to trial inclusion they will be considered as baseline conditions and should be collected in the eCRF only. All (S)AEs, including those persisting after a patient's end of trial, must be followed up until they have resolved, have been assessed as "chronic" or "stable", or no further information can be obtained.

Pregnancy

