Urine pregnancy testing should be done prior to study drug administration. Study drug should only be administered in case of a negative test result. In case of a positive urine pregnancy test, a serum pregnancy test will be done. Women who underwent tubal ligation are still considered of childbearing potential and pregnancy testing is necessary as well. The testing schedule is specified in the [Flow Chart](#). The patient will also be asked about their pregnancy status at the End of Study Safety Phone Call.

In rare cases, pregnancy might occur in a clinical trial. Once a patient has been enrolled in the clinical trial and has taken trial medication, the investigator must report any drug exposure during pregnancy in a trial participant immediately (within 24 hours) by means of Part A of the Pregnancy Monitoring Form to the sponsor's unique entry point.

The outcome of the pregnancy associated with the drug exposure during pregnancy must be followed up and reported to the sponsor's unique entry point on the Pregnancy Monitoring Form for Studies (Part B).

The ISF will contain the Pregnancy Monitoring Form for Studies (Part A and B).

As pregnancy itself is not to be reported as an AE, in the absence of an accompanying SAE and/or AESI, only the Pregnancy Monitoring Form for Studies and not the SAE form is to be completed. If there is an SAE and/or AESI associated with the pregnancy an SAE form must be completed in addition.

Exemptions to SAE reporting

For this study there are no exemptions to SAE reporting.

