7.3.4 Safety analyses

Adverse events will be coded using the Medical Dictionary for Drug Regulatory Activities (MedDRA). Standard BI summary tables and listings will be produced. All adverse events with an onset between start of treatment and end of the residual effect period (REP), a period of 16 weeks after the last dose of trial medication, will be assigned to the on-treatment period for evaluation.

All treated patients will be included in the safety analysis. In general, safety analyses will be descriptive in nature and will be based on BI standards. No hypothesis testing is planned.

Statistical analysis and reporting of adverse events will concentrate on treatment-emergent adverse events, i.e. all adverse events occurring between start of treatment and end of the REP. Adverse events that start before first drug intake and deteriorate under treatment will also be considered as 'treatment-emergent'.

[figure not shown]
Frequency, severity, and causal relationship of adverse events will be tabulated by system organ class and preferred term after coding according to the current version of the Medical Dictionary for Drug Regulatory Activities (MedDRA) at database lock.

[figure not shown]
Laboratory data will be analysed both quantitatively as well as qualitatively. The latter will be done via comparison of laboratory data to their reference ranges. Values outside the reference range as well as values defined as clinically relevant will be summarised. Treatment groups will be compared descriptively with regard to distribution parameters as well as with regard to frequency and percentage of patients with abnormal values or clinically relevant abnormal values.

Vital signs, physical examinations, or other safety-relevant data observed at screening, baseline, during the course of the trial and at the end-of-trial evaluation will be assessed with regard to possible changes compared to findings before start of treatment.

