7.8.1 Adverse events

AEs will be coded with the most recent version of MedDRA.

The analyses of AEs will be descriptive in nature. All analyses of AEs will be based on the number of patients with AEs and not on the number of AEs. System organ classes (if applicable) will be sorted according to the standard sort order specified by the EMA, preferred terms (if applicable) will be sorted by total frequency (within system organ class) across all treatment arms.

The analyses of AEs will be performed for double-blind period and for the re-allocation period separately.

For further details on summarization of AE data, please refer to “Analysis and Presentation of Adverse Event data from Clinical Trials” [BI-KMED-BDS-HTG-0066] (7) and “Handling of missing and incomplete AE dates” [BI-KMED-BDS-HTG-0035] (4).

The analysis of AEs will be based on the concept of treatment emergent AEs. If only the start date of an AE is collected (without start time), any AE occurrence on the same day as the first BI 655130 administration will be assigned to the on-treatment phase.

An overall summary of AEs will be presented by treatment.

This overall summary will include summary statistics for the class of other significant AEs (sponsor definition based on ICH E3 (9)) and for the class of AESIs.

The following is considered an AESI in this trial:

- Hepatic injury
- Infusion reactions including anaphylactic reaction
- Severe infections
- Opportunistic and mycobacterium tuberculosis infections

The investigator has to classify on the eCRF whether an observed AE was an AESI or not. Only those AEs that are indicated by the investigator as AESI in the eCRF will be analysed in this category.

Based on the specification provided in ICH E3 (9), the sponsor has defined AEs which are to be classified as ‘other significant’. These will include those non-serious AEs which were reported with ‘action taken = Drug withdrawn’ or ‘action taken = Dose reduced’.

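### Worsening of atopic dermatitis counts as an adverse event, and the SAP plans no any-AE or maximum-grade summary without it, so those totals mix lack of efficacy with toxicity

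*Protocol*

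**What the plan says.** Protocol 2.1.1 names safety and tolerability as the main objective, to be analysed descriptively. Protocol 3.1 gives the basis: "Safety and tolerability will be evaluated based on AE data collected and physical examination at every visit".

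On recording, Protocol 5.2.5.2 states "The following should also be recorded as an (S)AE in the CRF and, if applicable, BI SAE form", and the first item listed is "Worsening of the underlying disease or of other pre-existing conditions". The same section adds "For this study there are no exemptions to SAE reporting". Protocol 7.3.4 concentrates the analysis on treatment-emergent events, from start of treatment to the end of the residual effect period.

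On tabulation, SAP 7.8.1 states "An overall summary of AEs will be presented by treatment" and "All analyses of AEs will be based on the number of patients with AEs and not on the number of AEs". It also plans:
- AEs by system organ class and preferred term, and by maximum RCTC grade;
- separate tables for drug-related AEs (the secondary safety endpoint), SAEs, AESIs, AEs leading to discontinuation, and 'other significant' AEs (non-serious events with drug withdrawn or dose reduced);
- user-defined AE concepts, none of which covers worsening of atopic dermatitis.

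No visible table removes disease worsening from an any-AE or severity count.

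**The concern.** In a placebo-controlled trial, a flare recorded as an AE is partly a measure of efficacy. The protocol foresees flares. Patients come off topical and systemic AD therapy before the first dose (3.3.3), standard-of-care escape treatment is allowed if the disease worsens (4.2.1), and unscheduled visits are provided for worsening (6.2.2.2). Because continuation on trial treatment is reconsidered after escape treatment (4.2.1), a flare can also reach the discontinuation or 'other significant' lines.

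If BI 655130 works, these events fall more often on placebo. The percentage of patients with any AE, and the distribution of maximum grade, then move in favour of BI 655130 for a reason unrelated to its toxicity. A genuine excess of other AEs would look smaller in those two summaries, or could disappear. The analysis is descriptive, so what is at stake is how the figures are read, not an error rate.

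**Working it through.** **Plan's own figure.** The documents give no AE or flare rate in atopic dermatitis to reproduce. The sample size does reproduce: placebo n = (1.645 + 0.842)² × 30² × (1 + 1/2) / 25² = 13.4, rounded up to 14, hence 42 in total (28/14), as in Protocol 7.7. The present point does not depend on it.

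**Inputs.**
- Planned arms: 30 active, 15 placebo (Protocol synopsis).
- Any-AE rates in the placebo-controlled PPP trial: 85.7% placebo, 89.5% in each active arm (Protocol 1.2.3). This is another disease, and these rates may include its own worsening events.
- Flare-AE rates, the 50%, 60% and 70% other-AE rates, and independence of flares and other AEs are assumptions.

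**Formula.** P(any AE) = 1 − (1 − o)(1 − f), where o is the probability of any other AE and f of a flare recorded as an AE. If o is the same in both arms, the false advantage for BI 655130 is (1 − o)(f_placebo − f_active).

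**No true difference, flares 40% placebo and 15% active.**
- o = 50%: placebo 1 − 0.5 × 0.6 = 70%; active 1 − 0.5 × 0.85 = 57.5%; false advantage 12.5 points.
- o = 85.7%: placebo 1 − 0.143 × 0.6 = 91.4%; active 1 − 0.143 × 0.85 = 87.8%; false advantage 0.143 × 0.25 = 3.6 points.

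With flares of 30% and 15% and o from 40% to 60%, it is 0.6 × 15 = 9 down to 0.4 × 15 = 6 points.

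**True 10-point excess** (other AEs 50% placebo, 60% active; flares 40% and 15%): placebo 70%, active 1 − 0.4 × 0.85 = 66%. The excess shows as a 4-point advantage.

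**True 20-point excess** (other AEs 50% placebo, 70% active). The last column is an exact binomial calculation for 15 and 30 patients.

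| Flares placebo / active | Any AE placebo / active | Visible excess | Chance observed active rate is no higher than placebo |
|---|---|---|---|
| none | 50.0% / 70.0% | 20.0 points | 12% |
| 20% / 5% | 60.0% / 71.5% | 11.5 points | 26% |
| 30% / 10% | 65.0% / 73.0% | 8.0 points | 34% |
| 40% / 10% | 70.0% / 73.0% | 3.0 points | 47% |

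With flares of 10% / 5% the excess is 16.5 points. It vanishes at f_placebo = 1 − 0.3(1 − f_active)/0.5, which is 43% if active flares are 5% and 46% if they are 10%.

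**PPP rates as background.** The 3.8-point excess becomes +1.5 (20% / 5%), +0.6 (30% / 10%) or −0.9 points (40% / 10%).

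**The case against.** The other side has several good points.

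- A reader might infer that flares enter every AE total. They do not. The drug-related endpoint counts them only if the investigator judges them related, and the SAE table only if serious. The AESI list in SAP 7.8.1 does not include AD worsening.
- A reader might infer that an excess of other AEs would be hidden altogether. The system organ class and preferred-term table shows AD terms on their own line, so an excess in another term stays visible. SAP 7 also lists individual patient data, with AE listings sorted by treatment. With about 45 patients, a count without flares could be rebuilt by hand. What stands against this is that overlapping patients cannot be separated in the preferred-term table itself, and choosing terms after unblinding is weaker than fixing them before.
- Safety does not rest on the any-AE percentage. Protocol 3.1 adds physical examination, Protocol 5.2 lists nine safety components, and no decision rule uses any-AE.
- The size rests on assumed flare rates and is small against the noise. One placebo patient is 1/15 = 6.7 points, and the standard error of a difference near 50% is √(0.25/15 + 0.25/30) = 16 points. This limits the importance of the point, but a systematic shift remains.
- The direction is conditional. Eczema was an AE in 2 of 7 GPP patients given BI 655130 (Protocol 1.2.3), so skin worsening might itself be an adverse reaction.
- SAP 7.8.1 refers to a sponsor guideline on AE summaries that is not available here, so the absence is established only for the visible text.

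The clause in Protocol 7.3.4, "Adverse events that start before first drug intake and deteriorate under treatment will also be considered as" treatment-emergent, is not needed for the argument. A flare recorded as an AE with onset after the first dose is treatment-emergent in any case.

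**Conclusion.** The concern holds for the overall any-AE summary and the maximum-RCTC-grade table. Flares must be recorded as AEs, both summaries include them, and no visible version leaves them out. If BI 655130 lowers the flare rate, both favour it for a reason other than toxicity. The discontinuation, 'other significant', SAE and drug-related lines are affected only where a flare meets the relevant criterion.

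The size cannot be read from the documents. Under independence, equal other-AE rates and flares of 40% and 15%, it is 12.5 points at a 50% background and about 3.6 points at 85.7%. The higher background comes from another disease, so neither figure is a forecast.

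The documents do not support the stronger conclusion that the trial cannot answer its safety question. The term-level tables, the listings and the other safety components remain. This is a gap in descriptive reporting, worth closing because it is cheap to close.

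**What to change.** In SAP 7.8.1, for the double-blind period:

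1. Keep every planned all-AE table. AE collection and reporting stay as they are.
2. Add the overall AE summary, the maximum RCTC grade table and the discontinuation line again, excluding preferred terms that denote worsening of atopic dermatitis.
3. Fix that term list in blinded review before the Week 16 database lock.
4. Show AD worsening as its own line by arm.
5. State that the two versions are read together, so that a drug-induced flare stays visible.

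The cost is some SAP wording, a short term list and a few repeated tables. The downside is some judgement about which terms denote AD worsening. Because skin worsening could be an adverse reaction, the version without these terms could understate harm if read alone.
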